## STATISTICAL ANALYSIS PLAN

H52	XXX.X (XX.X)	XX.X (XX.X)	0.XXX									
H60	XXX.X (XX.X)	XXX.X (XX.X)	0.XXX									
H64	XXX.X (XX.X)	XXX.X (XX.X)	0.XXX									

**3.6 Assessing and comparing *P. falciparum* parasite clearance rate, additional parameters of parasite clearance dynamics and fever clearance time of standard ACTs and matching TACTs.**

Parasite clearance half-life, proportion of subjects with microscopically detectable *P. falciparum* parasitaemia at Day 3 and fever clearance time (i.e. the time taken for the tympanic temperature to fall below 37.5 °C in patients who were febrile at inclusion) will be summarized and presented in table 9 below. In addition, proportion of subjects with gametocytaemia during and after treatment stratified by presence of gametocytes at enrolment will be presented in tables 9 and 10 below.

**Table 9. Parasite clearance half-life, microscopy *P. falciparum* positivity and fever clearance time (up to H72 vs after H72)**

Arms	Median Time (hours) to Resolution of Fever (range) *	Median Parasite Clearance Half-Life in hours (range) **	Median Time (hours) to 50% Parasite Clearance (range) **	Median Time (hours) to 90% Parasite Clearance (range) **	Parasite Clearance Half-Life >5 hours, (n/N) % (95% CI) **	Positive for Parasitaemia on day 3, (n/N) % (95% CI) ***
AL based overall	XX.X (XX.X-XX.X)	XX.X (XX.X-XX.X)	XX.X (XX.X-XX.X)	XX.X (XX.X-XX.X)	(XX/XX) X(X-X)	(XX/XX) X(X-X)
AL+AQ	XX.X (XX.X-XX.X)	XX.X (XX.X-XX.X)	XX.X (XX.X-XX.X)	XX.X (XX.X-XX.X)	(XX/XX) X(X-X)	(XX/XX) X(X-X)
AL+Placebo	XX.X (XX.X-XX.X)	XX.X (XX.X-XX.X)	XX.X (XX.X-XX.X)	XX.X (XX.X-XX.X)	(XX/XX) X(X-X)	(XX/XX) X(X-X)
ASMQ based overall	XX.X (XX.X-XX.X)	XX.X (XX.X-XX.X)	XX.X (XX.X-XX.X)	XX.X (XX.X-XX.X)	(XX/XX) X(X-X)	(XX/XX) X(X-X)
ASMQ +PPQ	XX.X (XX.X-XX.X)	XX.X (XX.X-XX.X)	XX.X (XX.X-XX.X)	XX.X (XX.X-XX.X)	(XX/XX) X(X-X)	(XX/XX) X(X-X)

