
Drugs
 
See Appendix 2 for dosing regimens
	
In Rwanda only:
 
Artemether-lumefantrine+placebo for 3 days.
 
VERSUS
 
Artemether-lumefantrine+amodiaquine for 3 days.
 
All other sites:
 
Artemether-lumefantrine+placebo for 3 days.
 
VERSUS
 
Artemether-lumefantrine+amodiaquine for 3 days.
 
VERSUS
 
Artesunate-mefloquine+placebo for 3 days
 
VERSUS
 
Artesunate-mefloquine+piperavaquine for 3 days
 
Primaquine
 
According to the WHO guideline, all subjects except children under 10 kilograms will also be treated with a single dose of primaquine according to the local requirements or guidelines and WHO treatments schedule as a gametocytocidal treatment. Primaquine will not be deployed in study sites with median to high levels of malaria

	transmission (estimated Annual Parasite Incidence (API) \geq 50 per 1000 population per year according to the WHO World Malaria Report 2017)
--	--

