**Table 2a Comparison of Day 42 PCR corrected Efficacy as proportions of Various ACTs with matching TACTs by sites**

## STATISTICAL ANALYSIS PLAN

Site	PCR corrected ACPR at day 42, n/N, (%)				Risk difference (95% CI, p-value)	
	AL+Placebo (N=XXXX)	AL+AQ (N=XXXX)	ASMQ+Placebo (N=XXXX)	ASMQ + PPQ (N=XXXX)	AL+Placebo vs AL+AQ	ASMQ+Placebo vs ASMQ+PPQ
Burkina Faso	XX/XXX (XX.X)	XX/XXX (XX.X)	XX/XXX (XX.X)	XX/XXX (XX.X)	XX.X (XX.X - XX.X, 0.XXX)	XX.X (XX.X - XX.X, 0.XXX)
DR Congo	XX/XXX (XX.X)	XX/XXX (XX.X)	XX/XXX (XX.X)	XX/XXX (XX.X)	XX.X (XX.X - XX.X, 0.XXX)	XX.X (XX.X - XX.X, 0.XXX)
Gambia	XX/XXX (XX.X)	XX/XXX (XX.X)	XX/XXX (XX.X)	XX/XXX (XX.X)	XX.X (XX.X - XX.X, 0.XXX)	XX.X (XX.X - XX.X, 0.XXX)
Guinea	XX/XXX (XX.X)	XX/XXX (XX.X)	XX/XXX (XX.X)	XX/XXX (XX.X)	XX.X (XX.X - XX.X, 0.XXX)	XX.X (XX.X - XX.X, 0.XXX)
Niger	XX/XXX (XX.X)	XX/XXX (XX.X)	XX/XXX (XX.X)	XX/XXX (XX.X)	XX.X (XX.X - XX.X, 0.XXX)	XX.X (XX.X - XX.X, 0.XXX)
Nigeria	XX/XXX (XX.X)	XX/XXX (XX.X)	XX/XXX (XX.X)	XX/XXX (XX.X)	XX.X (XX.X - XX.X, 0.XXX)	XX.X (XX.X - XX.X, 0.XXX)
Tanzania	XX/XXX (XX.X)	XX/XXX (XX.X)	XX/XXX (XX.X)	XX/XXX (XX.X)	XX.X (XX.X - XX.X, 0.XXX)	XX.X (XX.X - XX.X, 0.XXX)
Rwanda	XX/XXX (XX.X)	XX/XXX (XX.X)	XX/XXX (XX.X)	XX/XXX (XX.X)	XX.X (XX.X - XX.X, 0.XXX)	XX.X (XX.X - XX.X, 0.XXX)
All sites	XX/XXX (XX.X)	XX/XXX (XX.X)	XX/XXX (XX.X)	XX/XXX (XX.X)	XX.X (XX.X - XX.X, 0.XXX)	XX.X (XX.X - XX.X, 0.XXX)

[figure not shown]
[figure not shown]

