## STATISTICAL ANALYSIS PLAN

**Table 6 Adverse events within the first 42 days**

Adverse events	AL+Placebo	AL+AQ	ASMQ+Placebo	ASMQ + PPQ
Number of subjects	XXXX	XXXX	XXXX	XXXX
Vomiting/number of treatments, n/N, (%)	XXX/XXXX (XX.X)	XXX/XXXX (XX.X)	XXX/XXXX (XX.X)	XXX/XXXX (XX.X)
Serious adverse events (SAEs), n/N, (%)	XX/XXXX (XX.X)	XX/XXXX (XX.X)	XX/XXXX (XX.X)	XX/XXXX (XX.X)
Possible, probable or definite drug related SAEs, n/N, (%)	XX/XXXX (XX.X)	XX/XXXX (XX.X)	XX/XXXX (XX.X)	XX/XXXX (XX.X)
QTc >500ms (H4 and H48/H52)	XXX/XXXX (XX.X)	XXX/XXXX (XX.X)	XXX/XXXX (XX.X)	XXX/XXXX (XX.X)
Change from baseline in haemoglobin at days 3, 7, 28 (stratified for G6PD status)	XXX/XXXX (XX.X)	XXX/XXXX (XX.X)	XXX/XXXX (XX.X)	XXX/XXXX (XX.X)
Grading of adverse events, n/N, (%)	1-2	3-4	1-2	3-4
Symptoms, n/N (%)	X/XX (X.X)	X/XX (X.X)	X/XX (X.X)	X/XX (X.X)
Headache	X/XX (X.X)	X/XX (X.X)	X/XX (X.X)	X/XX (X.X)
Fatigue	X/XX (X.X)	X/XX (X.X)	X/XX (X.X)	X/XX (X.X)
Abdominal pain	X/XX (X.X)	X/XX (X.X)	X/XX (X.X)	X/XX (X.X)
Loss of appetite	X/XX (X.X)	X/XX (X.X)	X/XX (X.X)	X/XX (X.X)
Nausea	X/XX (X.X)	X/XX (X.X)	X/XX (X.X)	X/XX (X.X)
Vomiting	X/XX (X.X)	X/XX (X.X)	X/XX (X.X)	X/XX (X.X)
Diarrhea	X/XX (X.X)	X/XX (X.X)	X/XX (X.X)	X/XX (X.X)
Itching	X/XX (X.X)	X/XX (X.X)	X/XX (X.X)	X/XX (X.X)
Dizziness	X/XX (X.X)	X/XX (X.X)	X/XX (X.X)	X/XX (X.X)
Blurred vision	X/XX (X.X)	X/XX (X.X)	X/XX (X.X)	X/XX (X.X)

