**Table 10 Gametocytaemia during and after treatment by gametocytes status at enrolment**

	Gametocytaemia, n (%), 95%CI)				p-value (AL+Placebo vs AL+AQ)	p-value (ASMQ+Placebo vs ASMQ+PPQ)
	AL+Placebo	AL+AQ	ASMQ+Placebo	ASMQ + PPQ		
Presence of gametocytes at enrolment	(N=XXXX)	(N=XXXX)	(N=XXXX)	(N=XXXX)		
During treatment	XX (XX.X, XX.X- XX.X)	XX (XX.X, XX.X- XX.X)	XX (XX.X, XX.X- XX.X)	XX (XX.X, XX.X- XX.X)	0.XXX	0.XXX
After treatment	XX (XX.X, XX.X- XX.X)	XX (XX.X, XX.X- XX.X)	XX (XX.X, XX.X- XX.X)	XX (XX.X, XX.X- XX.X)	0.XXX	0.XXX
Absence of gametocytes at enrolment	(N=XXXX)	(N=XXXX)	(N=XXXX)	(N=XXXX)		
During treatment	XX (XX.X, XX.X- XX.X)	XX (XX.X, XX.X- XX.X)	XX (XX.X, XX.X- XX.X)	XX (XX.X, XX.X- XX.X)	0.XXX	0.XXX
After treatment	XX (XX.X, XX.X- XX.X)	XX (XX.X, XX.X- XX.X)	XX (XX.X, XX.X- XX.X)	XX (XX.X, XX.X- XX.X)	0.XXX	0.XXX

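### Table 10 compares gametocyte carriage between ACT and TACT over all sites without separating sites that give gametocytocidal primaquine from those that do not: no bias, but a null result could not be interpreted.

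*SAP*

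**What the plan says.** Protocol sections 4.2 and 5.2 list gametocyte carriage among the secondary efficacy measures to be compared between arms. SAP section 3.6 carries this over: "In addition, proportion of subjects with gametocytaemia during and after treatment stratified by presence of gametocytes at enrolment will be presented" (Tables 9 and 10). Table 10, titled "Gametocytaemia during and after treatment by gametocytes status at enrolment", has four arm columns, rows for during and after treatment, and one p-value for each matching ACT–TACT pair. It has no site rows and no primaquine split. Tables 2a to 5b, by contrast, are laid out by site with an all-sites row; Table 2a, for example, is headed "Comparison of Day 42 PCR corrected Efficacy as proportions of Various ACTs with matching TACTs by sites". For proportions, Protocol section 15.2.1 names chi-squared or Fisher's exact tests, without stratification.

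Primaquine use differs by site. Protocol section 7 gives it as a gametocytocidal dose where annual parasite incidence is below 50 per 1000, and the Synopsis says it is not deployed at or above that level. At sites that use it, "all subjects except children under 10 kilograms will also be treated with a single dose of primaquine". Appendix 2 times the dose at 24 h. The SAP names primaquine only in the exploratory haemolysis objective (section 2.1.4). Neither document says which or how many sites use it.

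**The concern.** Primaquine is given to clear gametocytes, and gametocyte carriage is the outcome in Table 10. At primaquine sites the table measures an ACT or TACT plus a gametocytocidal drug. At the other sites it measures the ACT or TACT alone. One pooled row averages the two.

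Two consequences follow. The pooled absolute difference then depends partly on how many participants come from low-transmission sites, which is a feature of recruitment and not of the drugs. And a pooled null has two explanations that the table cannot separate: the third drug does not affect carriage, or primaquine removed gametocytes in both arms and left little to compare. Both the during-treatment and the after-treatment rows are affected, because the 24 h dose falls inside the three-day treatment course.

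**Working it through.** **Inputs from the documents.** Each matching pair has 72 ACT and 144 TACT subjects per site (Protocol 15.1). The AL pair runs at 8 sites: 8 × 72 = 576 and 8 × 144 = 1,152. The ASMQ pair runs at 7 sites: 7 × 72 = 504 and 7 × 144 = 1,008. Together 576 + 1,152 + 504 + 1,008 = 3,240, the stated total. The plan states no carriage rate, effect size or power for this endpoint, so it has no figure to reproduce.

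**Assumptions, not in the documents.** Carriage without primaquine is 15% (ACT) and 10% (TACT). With primaquine there are two cases: (A) 3% in both arms; (B) carriage multiplied by 0.3 in both arms, giving 4.5% and 3%. The share f of participants who get primaquine is 12.5%, 25% or 50%.

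**Formulas.** Pooled carriage in an arm = (1 − f) × p(no primaquine) + f × p(primaquine). Power = Φ[(Δ − 1.96 √(p̄(1 − p̄)(1/n₁ + 1/n₂))) / √(p₁(1 − p₁)/n₁ + p₂(1 − p₂)/n₂)], two-sided 5%, where Δ = p₁ − p₂ and p̄ is the carriage over both arms together. With f = 0 this gives 85% for 576 vs 1,152.

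Example, case A, f = 25%: ACT 0.75 × 15 + 0.25 × 3 = 12.0%; TACT 0.75 × 10 + 0.25 × 3 = 8.25%; difference 3.75 points.

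| Case | f | Pooled difference (points) | Risk ratio | Power, pooled | Power, no-primaquine stratum alone |
|---|---|---|---|---|---|
| A | 12.5% | 4.4 | 0.68 | 78% | 80% |
| A | 25% | 3.8 | 0.69 | 70% | 74% |
| A | 50% | 2.5 | 0.72 | 47% | 57% |
| B | 12.5% | 4.6 | 0.67 | 81% | 80% |
| B | 25% | 4.1 | 0.67 | 77% | 74% |
| B | 50% | 3.3 | 0.67 | 66% | 57% |

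The undiluted values are 5.0 points and a risk ratio of 10/15 = 0.67. The absolute difference shrinks in both cases. The risk ratio moves only in case A.

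**Stratified test.** The Cochran-Mantel-Haenszel statistic sums W(p₁ − p₂) over strata, with W = n₁n₂/(n₁ + n₂) and null variance ΣWp̄(1 − p̄). With two strata (primaquine, no primaquine) as a stand-in for site, power at f = 12.5%, 25% and 50% is 79%, 70% and 48% in case A and 82%, 78% and 67% in case B. Before rounding, each is 0.3 to 1.0 point above the pooled test.

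**Limit of these figures.** No row of Table 10 has 576 vs 1,152 subjects, because every row is split by enrolment gametocytes. If 10% carried gametocytes at enrolment (assumed), that row would hold about 58 vs 115, and power at 15% vs 10% would be below 20% even without any primaquine. The table above shows the direction and relative size of the dilution, not the power of a Table 10 row.

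**The case against.** The strongest objection is that nothing here is biased. Primaquine is given by site policy and weight, not by arm, and Protocol section 9.4 provides randomisation envelopes for each site, with a 1:2 ratio within each pair. The pooled contrast therefore validly estimates the effect under local primaquine policy, and the SAP uses the stratifier that the protocol prespecified. This stands. A reader might infer confounding, but the documents do not support that.

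A reader might also conclude that the no-primaquine stratum should supply the headline estimate. That holds up only in case A. In case B the stratum has less power than the pooled comparison at every share examined, and no figure in the documents favours one case over the other.

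Splitting by primaquine actually received is also tempting. But the dose comes at 24 h, after randomisation, and receipt could depend on early vomiting or withdrawal. Protocol section 19.4.5 reports slightly more early vomiting with the TACTs studied before. Such a split would give up the protection of randomisation, and it would place children under 10 kg at primaquine sites with the non-primaquine sites.

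Finally, a reader might extend the point to the G6PD-stratified haemoglobin row in SAP Table 6. That row serves the ACT vs TACT safety endpoint. The primaquine haemolysis objective has its own haematocrit endpoint by location, arm and G6PD status, with a separate plan promised in SAP section 3.11.

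The objection does not remove the problem of interpretation: the planned layout gives no means of telling the two explanations of a null apart.

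**Conclusion.** The point holds as a low-cost improvement to a secondary analysis, not as an error or a source of bias. Table 10 averages over two regimens on an outcome that one of them is designed to change. The absolute difference is attenuated wherever primaquine narrows the gap between arms. In the illustration it falls from 5.0 points to between 2.5 and 4.6, depending on the primaquine share and on how primaquine acts. These figures rest entirely on assumed carriage rates and shares. Whether the risk ratio is also attenuated depends on whether primaquine acts by the same factor in both arms, which the documents do not settle. Nor do they support discarding primaquine sites.

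**What to change.** In Table 10, replace the unstratified p-value with a Cochran-Mantel-Haenszel test stratified by site, within each enrolment-gametocyte row and keeping all sites. This matches the by-site randomisation and lost no power in the cases examined.

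Add a split by primaquine eligibility as fixed before randomisation: site primaquine policy together with baseline weight (under 10 kg vs 10 kg or more), not primaquine received. Report the ACT–TACT risk difference and risk ratio in each stratum.

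The SAP should list which sites use primaquine. Before eligibility is coded, one inconsistency must be reconciled: the Appendix 2 primaquine table has a row for under 25 kg with no lower limit, whereas the Synopsis and Protocol section 7 exclude children under 10 kg.

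Cost: one more table layout and smaller strata, some of which may have too few gametocyte carriers for a stable ratio. No additional data collection is needed. The change is best made before unblinding, since a later split would look post hoc.

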## STATISTICAL ANALYSIS PLAN

ASMQ +Placebo	XX.X (XX.X-XX.X)	XX.X (XX.X-XX.X)	XX.X (XX.X-XX.X)	XX.X (XX.X-XX.X)	(XX/XX) X(X-X)	(XX/XX) X(X-X)
------------------	------------------	------------------	------------------	------------------	----------------	----------------

**Table 10 Gametocytaemia during and after treatment by gametocytes status at enrolment**

	Gametocytaemia, n (%), 95%CI)				p-value (AL+Placebo vs AL+AQ)	p-value (ASMQ+Placebo vs ASMQ+PPQ)
	AL+Placebo	AL+AQ	ASMQ+Placebo	ASMQ + PPQ		
Presence of gametocytes at enrolment	(N=XXXX)	(N=XXXX)	(N=XXXX)	(N=XXXX)		
During treatment	XX (XX.X, XX.X- XX.X)	XX (XX.X, XX.X- XX.X)	XX (XX.X, XX.X- XX.X)	XX (XX.X, XX.X- XX.X)	0.XXX	0.XXX
After treatment	XX (XX.X, XX.X- XX.X)	XX (XX.X, XX.X- XX.X)	XX (XX.X, XX.X- XX.X)	XX (XX.X, XX.X- XX.X)	0.XXX	0.XXX
Absence of gametocytes at enrolment	(N=XXXX)	(N=XXXX)	(N=XXXX)	(N=XXXX)		
During treatment	XX (XX.X, XX.X- XX.X)	XX (XX.X, XX.X- XX.X)	XX (XX.X, XX.X- XX.X)	XX (XX.X, XX.X- XX.X)	0.XXX	0.XXX
After treatment	XX (XX.X, XX.X- XX.X)	XX (XX.X, XX.X- XX.X)	XX (XX.X, XX.X- XX.X)	XX (XX.X, XX.X- XX.X)	0.XXX	0.XXX

**3.7 Pharmacokinetic and pharmacodynamic interactions between antimalarials in ACT and TACTs**

A detailed analysis plan will be prepared separately.

**3.8 Molecular genetic and transcriptomic correlates for artemisinin and partner drug resistance of the infecting *P. falciparum* strains and to assess their ex vivo and in vitro drug susceptibility**

A detailed analysis plan will be prepared separately.

**3.9 In vitro sensitivity of *P. falciparum* to artemisinins and partner drugs according to study sites and genotype**

A detailed analysis plan will be prepared separately.

## STATISTICAL ANALYSIS PLAN

**3.10 The selective effect of ACTs versus TACTs on parasites carrying mutations associated with resistance to antimalarial drugs**

Recurrent infections with parasites carrying mutations of known functional significance and specimens collected at baseline with parasites carrying mutations of known functional or operational significance (pfkelch13, pfcrt, pfmdr1, pfdhfr, pfhdps, pfplasmepsin2, partial or complete deletions of pfhrp2 and other current parasite genetic markers associated with resistance or identified over the course of the study) will be summarized as proportions of the total number of samples per site (% and 95% confidence interval) as in table 11.

**Table 12 Recurrent infections and specimens collected at baseline with parasites carrying mutations of known functional significance**

	AL+Placebo (N=XXXX)	AL+AQ (N=XXXX)	ASMQ+Placebo (N=XXXX)	ASMQ + PPQ (N=XXXX)	p-value (AL+Placebo vs AL+AQ)	p-value (ASMQ+Placebo vs ASMQ+PPQ)
Reinfections, n (% CI 95%)	XX.X (XX.X- XX.X)	XX.X (XX.X-XX.X)	XX.X (XX.X- XX.X)	XX.X (XX.X- XX.X)	0.XXX	0.XXX
Pf kelch13, n (% CI 95%)	XX.X (XX.X- XX.X)	XX.X (XX.X-XX.X)	XX.X (XX.X- XX.X)	XX.X (XX.X- XX.X)	0.XXX	0.XXX
Pf crt, n (% CI 95%)	XX (XX.X, XX.X-XX.X)	XX (XX.X, XX.X- XX.X)	XX (XX.X, XX.X- XX.X)	XX (XX.X, XX.X- XX.X)	0.XXX	0.XXX
Pf mdr1, n (% CI 95%)	XX.X (XX.X- XX.X)	XX.X (XX.X-XX.X)	XX.X (XX.X- XX.X)	XX.X (XX.X- XX.X)	0.XXX	0.XXX
Pf dhfr, n (% CI 95%)	XX.X (XX.X- XX.X)	XX.X (XX.X-XX.X)	XX.X (XX.X- XX.X)	XX.X (XX.X- XX.X)	0.XXX	0.XXX
Pf dhps, n (% CI 95%)	XX.X (XX.X- XX.X)	XX.X (XX.X-XX.X)	XX.X (XX.X- XX.X)	XX.X (XX.X- XX.X)	0.XXX	0.XXX
Pf Plasmepsin 2, n (% CI 95%)	XX.X (XX.X- XX.X)	XX.X (XX.X-XX.X)	XX.X (XX.X- XX.X)	XX.X (XX.X- XX.X)	0.XXX	0.XXX
Partial or complete deletions of PF hrp2, n (%, CI 95%)	XX.X (XX.X- XX.X)	XX.X (XX.X-XX.X)	XX.X (XX.X- XX.X)	XX.X (XX.X- XX.X)	0.XXX	0.XXX
Others, n (% CI 95%)	XX.X (XX.X- XX.X)	XX.X (XX.X-XX.X)	XX.X (XX.X- XX.X)	XX.X (XX.X- XX.X)	0.XXX	0.XXX

---

## STATISTICAL ANALYSIS PLAN

---

### 3.11

#### **Change in hematocrit over time according to geographical location and study arm, stratified for G6PD status**

Change in hematocrit on day 1 to 7, 14, 21, 28, 35 and 42 according to geographical location and study arm, stratified for G6PD status will be summarized and analyzed. A detailed analysis plan will be prepared separately.

### 3.12 Correlation between the host genotype (e.g., CYP2D6, CYP3A4, KCNQ1/LQT1, KCNH2/LQT2, SCN5A/LQT3) and the pharmacokinetics and pharmacodynamics of antimalarials.

A detailed analysis plan will be prepared separately.

### 3.13 Correlations between the place of residence, work, recent travel history assessed by interview and mobile phone records to identify behaviours and risk factors associated with malaria infection.

A detailed analysis plan will be prepared separately.

### 3.14 Assess new methods for determination of gametocytaemia, parasite phenotypes and genotypes

A detailed analysis plan will be prepared separately.

### 3.15 Correlation between specific antibody titres and measures of drug efficacy

A detailed analysis plan will be prepared separately.

### 3.16 Accuracy of SNPs assessment from dry blood spots versus from whole genome sequencing in leukocyte depleted blood samples

A detailed analysis plan will be prepared separately.

### 3.17 Candidate markers of resistance identified through genome wide association studies with in vivo or in vitro parasite drug sensitivity phenotypes

A detailed analysis plan will be prepared separately.

---

## STATISTICAL ANALYSIS PLAN

---

### **3.18 Correlation between qPCR based versus microscopy based assessments of parasite clearance dynamics**

A detailed analysis plan will be prepared separately.

### **3.19 Correlation of parasite clearance metrics as assessed by microscopy versus digital microscopy**

A detailed analysis plan will be prepared separately.

### **3.20 Comparison of transcriptomic patterns of drug sensitive and resistant parasites before treatment and 6, 12 and 24 hours after start of treatment**

A detailed analysis plan will be prepared separately.

### **3.21 Levels of RNA transcription coding for male or female specific gametocytes at admission up to day 14, stratified by the presence of gametocytes at enrolment**

A detailed analysis plan will be prepared separately.
